Summary, Benefit to Stakeholders, and Aims: Teachers lack the knowledge and skills to support the learning of students with excessive anxiety who have, or at risk of developing, an IDEA disability. Excessive student anxiety is a common problem that severely impairs short and long term academic functioning and increases teacher burden. Conversely, reducing student anxiety has been associated with improvement in educational functioning. Because anxiety manifests daily in the classroom, teachers are in an ideal position to identify and help students manage their anxiety. One universal intervention for anxiety reduction exists, but its feasibility and efficacy are not established. The aims of this application are to address this gap in teacher training. Specifically, the aims of this proposal include: Aim 1) to develop the *Teacher Anxiety* Program for Elementary Students (TAPES) and assess its usability, acceptability and feasibility; Aim 2) to determine whether teachers can implement TAPES with high fidelity and quality; Aim 3) to examine the impact of TAPES, compared to a standard professional development condition, on teacher a) knowledge and b) use of anxiety reduction strategies with students with excessive anxiety (Primary Outcomes); and Aim 4) to examine the impact of TAPES on student outcomes. Exploratory aims will examine the mediators (proposed in the theory of change, see Figure 1 in Appendix) and predictors and moderators of TAPES impact on teachers knowledge and skill. If effective, TAPES has the potential to directly benefit: 1) teachers--by providing training in an important and relevant, but neglected area that will enhance their professional development and effectiveness in the classroom; and 2) children--by reducing their anxiety and improving their educational, social, and behavioral functioning. This development process will be led by a research team with over two decades of experience developing and evaluating feasible and effective trainings and interventions for school personnel ([name] et al., 2012, 2016). It will also be supported by a Development Team (DT) comprised of national teacher training experts, teachers, and CT State Board of Education representatives.

Preliminary study: Survey of current teacher practices for anxious youth. In preparation for the current application, we undertook a survey with 13 CT elementary teachers and school

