personnel to assess the significance and feasibility of the proposed training. Specifically, participants were asked to complete a 26 item survey that assessed: 1) the prevalence and negative impact of anxiety in the classroom, 2) teacher preparedness for managing anxiety, and 3) the feasibility of a school-home intervention (including associated trainings, coaching, fidelity monitoring, etc.). Results of the survey were as follows: With respect to perceived prevalence and impact of anxiety within the classroom, teachers reported that an average of 38.5% of children in their class had excessive anxiety (range 10 - 50%). Sixty-two percent of the respondents indicated that anxiety "often" negatively impacts the classroom and 77% indicated that reducing anxiety was a very important priority. Regarding teacher preparedness for managing anxiety, 54% felt confident in identifying the signs of anxiety in their classroom (46% did not!). *None (0%) of the teachers/staff received reported receiving specific training in anxiety* reduction techniques. All respondents (100%) endorsed an interest in learning anxiety reduction skills. With respect to the feasibility of the proposed TAPES training and meeting format, 90.9% of teachers reported they could hold conjoint meetings monthly or more often. In terms of length of conjoint meetings, 39% said they could meet with parents for approximately 45 minutes and 31% said 30 minutes. Teachers reported that they would be willing to dedicate a full day (53.8%), a half day (30.8%) or three hours (15.4%) to learning anxiety reduction techniques. All teachers (100%) thought that parents would be motivated to work with teachers to reduce their children's anxious behavior and improve their classroom behavior.

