The importance of close interaction between school and home settings has been emphasized for decades and psychosocial interventions that incorporate both parent and school components have been successful in improving academic and behavioral outcomes, though the targets have primarily been externalizing behaviors (Sheridan, Clarke, & Burt, 2008). Moreover, data from school-home intervention studies reveal that improvements in teacher-reported relationships with parents mediate intervention effects on positive changes in child outcomes, highlighting the critical role of training teachers in how to develop this collaborative relationship. TAPES Training Format and Implementation: Students' primary teacher will participate in a one-day training (approximately 8 hours). One of the most important strategies for ensuring that TAPES is implemented with high fidelity is appropriate training and ongoing consultation. Training strategies will be based on published guidelines (Beidas & Kendall, 2010) and will include active/experiential learning strategies, opportunities for observation (via video clips), live modeling and role plays, and coached practice. Ongoing performance feedback and consultation has been found to enhance learning (Fixsen et al., 2005; Sholomskas et al., 2005) and is related to higher fidelity (Sholomskas et al., 2005). Thus, teachers will be offered 30-minutes of weekly consultation by Drs. [name] and [name] for each active TAPES students. Consultation will include case review, skill rehearsal, problem-solving obstacles, and feedback regarding performance based on audiotaped sessions. Meetings will be held in person, over the phone, or via Skype at times convenient for teachers. After each teacher identifies their first child, the PIs will attend one conjoint meeting in order to provide performance feedback (all conjoint meetings are audiotaped for fidelity). The PIs will also provide in classroom coaching for 30-minutes for each student enrolled. Training materials will be available on the internet or thumb drive for reference.

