
Phase 1 - Recruitment, Randomization, Training, Student Screening, and Baseline

Evaluations: In Phase 1, teachers will be randomly selected from the pool of interested participants and randomized to TAPES or TAT. Once randomized, teachers will complete their assigned training. Teachers will then identify potentially eligible students from their classes and provide information about the study to their parents. Interested parents will contact study staff and complete a brief phone screen. Students who appear eligible based on the phone screen (e.g.,

have elevated anxiety; are in elementary school) will be invited to complete informed consent and a full baseline evaluation with an IE (see Table 1 for measures). Families who "pass" the baseline evaluation (i.e., student obtains a *t* score of 60 on Spence Children's Anxiety Scale (SCAS) and/or a CSR of at least 3 on the ADIS-V) will be considered eligible (see Inclusion/Exclusion criteria below).

Phase 2 – TAPES/TAT Implementation: Teachers will implement TAPES or TAT depending on their random assignment over 8 weeks from child enrollment.

Phase 3 - Post- and Follow-up Evaluations: At the end of the 8 weeks, teachers and children in both groups will complete a post evaluation (see Table of Measures). Teachers, students, and parents will complete a TAPES satisfaction measure and provide feedback to enhance the protocol. Teachers will complete an exit interview. Students who need mental health services will be referred to the school counselor or community provider for treatment. A 3 month follow-up evaluation to assess sustained use of TAPES/TAT skills will be conducted.

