TAT: TAT is a 3-hour didactic training on student anxiety that the PIs use in their ongoing school-based studies for school clinicians and nurses (modified for teachers). The TAT content will include information on the signs, causes, consequences, and effective interventions for student anxiety. As noted earlier, this control condition was selected to enhance teacher recruitment and mimic the format of teacher professional development trainings in CT. Thus, TAT will provide a credible and acceptable control. An added value of this proposal will be to examine the impact of TAT on teacher behavior and child outcomes relative to TAPES. Independent Evaluator (IE) Training. IEs will have a masters or doctoral degree in a relevant child mental health field and experience with conducting diagnostic assessments with anxious youth. Training and certification of IEs will include completion of: 1) didactic training that includes review and practice of all assessment measures and study procedures by the PIs, 2) review of ADIS videotaped administrations by a senior interviewer, 3) achieving inter-rater reliability (kappa) of .85 for the severity ratings on 3 cases (live or with videotapes) and 4) administration of the ADIS in the presence of a senior interviewer. All assessments will be videotaped and a random 15% of tapes will be evaluated for interrater reliability (i.e., for the severity ratings).

Measures. The selection of proposed measures to be used in Stages 2 and 3 was guided by the best available measures for the study aims and proposed theory of change, and participant burden. Measures, informants, and time points are listed in Table 1. Data will be collected from multiple informants (e.g., teacher, IEs, parent, child) using multiple formats (e.g., classroom observations, rating scales, interviews, school records). *Many of the measures were used in the*

PI's previous school-based intervention development studies and will be modified for TAPES. The assessment battery will also be modified based on DT and open trial feedback. Measures to be developed and used in the sub-study are also included in this section.

Primary Outcomes: Teacher Knowledge and Skills

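### TAPES training takes about 8 hours and TAT 3, yet availability for either is not confirmed before allocation, so teacher loss could fall more on the TAPES arm

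*Combined protocol and SAP*

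**What the plan says.** **Training length.** TAPES Training Format and Implementation: "Students' primary teacher will participate in a one-day training (approximately 8 hours". Intervention Conditions, TAT: "TAT is a 3-hour didactic training on student anxiety".

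**Order of events.** In Stage 3, Phase 1, "teachers will be randomly selected from the pool of interested participants and randomized to TAPES or TAT". Then "Once randomized, teachers will complete their assigned training". Only after that do teachers identify students in their classes.

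**Feasibility evidence.** Under Preliminary study, "we undertook a survey with 13 CT elementary teachers and school" personnel. Respondents were "willing to dedicate a full day (53.8%), a half day (30.8%) or three hours (15.4%) to learning anxiety reduction techniques".

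**Eligibility and replacement.** Teacher Inclusion Criteria asks only for a primary regular or special education teacher employed in the state's public schools. Teacher Recruitment and Retention allows withdrawn teachers to be replaced. It does not say whether this applies after randomisation, into which arm, or how the replaced teacher is analysed.

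**Existing protections.** District and principal support is required before teachers are recruited (Theory of teacher behavior change). Two open trials with 15 teachers test the training before the RCT. Teachers are paid $50 for attending training. Rates of and reasons for attrition are tracked. Missing Data commits to intention-to-treat, all available data, multiple imputation and sensitivity analyses.

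**The concern.** The two arms make very different demands at the first step after allocation. A teacher who can spare three hours but not a full day could complete TAT, but could not complete TAPES. If such teachers leave once they learn their arm, the TAPES teachers who remain are a selected subset while the TAT arm stays intact. Randomisation then no longer protects the comparison of the two primary teacher outcomes, knowledge and classroom skills.

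The replacement rule could hide this. Putting a willing volunteer in place of a TAPES decliner would restore the count of 20 but not the comparability of the arms.

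**Working it through.** **1. The survey figures.** Out of 13, 7/13 = 53.8%, 4/13 = 30.8% and 2/13 = 15.4%. They sum to 13, so the answers are mutually exclusive. (Another item's 90.9% fits 10 of 11, so not every item need have 13 answers, but this one does.) Those naming less than a full day: 4 + 2 = 6, and 6/13 = 46.2%, exact (Clopper-Pearson) 95% CI 19.2% to 74.9%. Those naming at least three hours: 13/13, exact 95% CI 75% to 100%.

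**2. Carried to the RCT, as illustration only.** The Randomization paragraph gives 20 teachers per arm. 20 × 6/13 = 9.2 TAPES teachers, with limits 20 × 0.192 = 3.8 and 20 × 0.749 = 15.0. The TAT counterpart is 0 of 20.

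**3. Selection shift.** Assume that the k least willing of 20 TAPES teachers are lost, that their data are lost entirely, and that willingness correlates ρ with the outcome. With retained share q = (20 − k)/20 and z the normal cut-point leaving q above it, the shift in the TAPES mean is ρ × φ(z)/q. The standard error of the arm difference rises by √[(1/(20 − k) + 1/20)/(2/20)].

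| k lost | q | Shift at ρ = 0.3 (SD) | SE ratio |
|---|---|---|---|
| 2 | 0.90 | 0.06 | 1.03 |
| 4 | 0.80 | 0.10 | 1.06 |
| 6 | 0.70 | 0.15 | 1.10 |
| 9 | 0.55 | 0.22 | 1.19 |

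At ρ = 0.5 and k = 9 the shift is 0.36 SD. As a cross-check, suppose decliners differ from attenders by 0.5 SD. The shift is then the refusal share × 0.5, or 0.05, 0.10, 0.15 and 0.23 SD at 10%, 20%, 30% and 46% refusal. For scale, the standard error with 20 per arm is √(2/20) = 0.32 SD, and the plan's knowledge effect is d = 1.19.

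**4. Power.** The plan claims 80% power at d = 1.19 with 20 per arm. A two-sided 0.05 t-test (sidedness is not stated) gives about 96%, so the claim holds as a minimum. Excluding 9 TAPES teachers (11 v 20) still leaves about 87%. If decliners instead stay in the analysis with no training effect, d becomes 1.19 × (1 − refusal share):

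| Refusal share | d | Power |
|---|---|---|
| 10% | 1.07 | 91% |
| 20% | 0.95 | 83% |
| 30% | 0.83 | 73% |
| 46% | 0.64 | 51% |

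Exclusion mainly risks bias; retention dilutes the effect. Preventing the loss avoids both.

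**5. What intention-to-treat can recover.** The Aim #3 skills model uses one rating per teacher and anxious student at baseline, post-intervention and follow-up. Students are found only after training, so a teacher who leaves before it forms no pair. Table 1 lists a pre-training classroom observation under Usability Measures, but that model does not use it. The plan does not say how either primary outcome is obtained from a teacher who declines training.

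**The case against.** **The survey is weak evidence about trial teachers.** A reader might infer that about 46% of TAPES teachers will refuse. The documents do not support that. The 13 respondents included other school personnel and were not trial volunteers. The question wording is not given, so treating a half-day answer as a ceiling is itself an inference. RCT teachers are volunteers and need number only 40 from a pool of over 460. The consent documents were not available, so what volunteers are told about training time cannot be checked. All of this stands.

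**Earlier drop-out does not point to TAPES.** A reader might take the Randomization section's account of drop-out in previous trials as support. Those who left were clinicians or nurses assigned to no training, and the two-active-arm design was chosen in response. If anything, that is loss from the arm offered less.

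**Safeguards exist.** Administrative support, open trials that may change the training, attrition tracking and the intention-to-treat commitment all help. None secures outcomes from a teacher who leaves before training, and none limits replacement.

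**The shift is near a worst case.** It assumes strict loss of the least willing, no data from them, and no adjustment. The knowledge model conditions on pre-training score, so only willingness's correlation with the remaining variation matters. Availability for a full day also need not mean greater skill or motivation, so the direction is assumed. This stands, and limits the weight of the figures.

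**Randomising before training is not itself a fault.** The training is the intervention, so allocation must come first. The gap is the missing confirmation before allocation.

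**Conclusion.** The point holds as a minor, cheaply closed gap. The documents establish the unequal demand (about 8 hours against 3), allocation before training, the absence in the available text of any prior confirmation of availability, and an unrestricted replacement rule. They also show that intention-to-treat, as planned, would not supply classroom-skill ratings for a teacher lost before training.

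They do not establish how many teachers would be lost, or that the result would favour TAPES. The shift of roughly 0.06 to 0.22 SD rests on an assumed 2 to 9 losses and an assumed correlation of 0.3, before baseline adjustment. It is smaller than the standard error of the arm difference and much smaller than the planned knowledge effect. A claim that the trial is biased towards TAPES would go beyond the evidence.

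**What to change.** In Stage 3, Phase 1 and in the teacher recruitment and inclusion text:

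1. Before the arm is drawn, have each teacher confirm that they can attend either training on the scheduled dates. Randomise only those who confirm.
2. Log those who cannot, with reasons, as Aim 1 feasibility data, so that this information is kept.
3. Limit replacement to before randomisation.
4. Seek the knowledge test and the classroom observation from every randomised teacher, attended or not, and analyse them as assigned. State how a rating from a teacher with no enrolled student enters the Aim #3 skills model. Analysis as assigned is already the plan's principle; the addition is collecting the data.

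**Cost.** One checklist item, a few protocol sentences, and some follow-up effort for non-attenders. Generalisability narrows slightly, to teachers who can spare a full day. If the survey share applied to volunteers, filling 40 RCT places would take 40 ÷ (7/13) = 74.3, so 75 volunteers. At the lower confidence limit of 25.1% it would take 40 ÷ 0.251, about 160. The plan expects more volunteers than places and can add districts. Training lengths need not change. The step does not address TAPES's later demands, such as conjoint meetings and weekly consultation, so attrition by arm should still be reported.
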